#### **9.4.1.2.2. Analyses of Additional Secondary Endpoints**

Additional secondary endpoints defined in [Table 4](#) will be analyzed as follows:

Time to response for each individual TMA parameter during the 26-week Treatment Period will be assessed in a similar manner as time to Complete TMA Response.

The binary additional secondary endpoints will be summarized by randomized treatment group by calculating the point estimate and 2-sided 95% CI for the response rate, based on exact confidence limits using the Clopper Pearson method. Treatment comparison of the response rate at all scheduled assessments during the 26-week randomized Treatment Period will be based on Cochran-Mantel-Haenszel test stratified by randomization stratification factors.

For continuous additional secondary endpoints, MMRM model will be used and similar statistics will be provided as described above.

For all parameters summarized during the Randomized Treatment Period other than eGFR, baseline is defined as the last non-missing assessment value prior to the start of study treatment (data from Screening or Day 1, prior to date of randomization).

For participants who require dialysis, change from baseline in dialysis requirements will be summarized.

#### **9.4.1.3. Multiplicity Adjustment**

The primary and key secondary efficacy analyses will use a hierarchical stepdown closed-testing procedure. If the null hypothesis for the primary efficacy estimand is rejected, the key secondary efficacy estimands will be tested in the following order until a non-significant test is observed, at which point no further testing of subsequent estimand will occur:

1. Time to Complete TMA Response during the 26-week randomized Treatment Period
2. Achievement of hematologic response at Week 26
3. Change from baseline in eGFR at Week 26
4. On dialysis at Week 26

#### **9.4.2. Safety Analyses**

All safety analyses will be performed on the Safety Set. Participants will be analyzed according to the study treatment they actually received.

#### **9.4.2.1. Adverse Events**

The following definitions will be used for AEs:

- Pretreatment AEs: Any AE that starts after providing informed consent, but before the first infusion of study drug
- Treatment-emergent adverse event (TEAE): Any AE that starts between the start of the first infusion of study drug and up to 8 months after the last infusion of study drug

- Treatment-emergent SAE (TESAE): A TEAE that meets the criteria for serious (Section 10.4.2)
- Post-treatment AEs: Any AE that starts 8 months or later after the last infusion of study drug

The incidence of TEAEs, TEAEs leading to withdrawal from the study, TEAEs leading to study drug discontinuation, and TESAEs will be summarized by treatment group. All AEs will be coded using the Medical Dictionary for Regulatory Activities (MedDRA), version 23.0 or higher, and will be summarized by System Organ Class and Preferred Term overall, by severity, and by relationship to study drug.

Detailed by-participant listings of TEAEs, TESAEs, related TEAEs, TEAEs leading to withdrawal from the study, and TEAEs leading to study drug discontinuation will be provided.

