### **8.4.1. Time Period and Frequency for Collecting AE and SAE Information**

All AEs and SAEs will be collected from the signing of the ICF until the EOS Visit. For participants who withdraw from the study during the Treatment Period, all AEs and SAEs should be collected through 8 weeks after last dose of study drug. For participants who discontinue study drug, but remain in the Follow-up Period, all AEs and SAEs will be collected through the EOS Visit.

All SAEs will be recorded and reported to Alexion or the designee immediately and under no circumstance should this exceed 24 hours, as indicated in Section 10.4. The Investigator, or designee, will submit any updated SAE data to Alexion within 24 hours of the date the study site became aware of the event.

Investigators are not obligated to actively seek AE or SAE data after conclusion of the study participation. However, if the Investigator learns of any SAE, including a death, at any time after a participant has concluded participation in the study, and he/she considers the event to be

reasonably related to the study drug or study participation, the Investigator must promptly notify Alexion.

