## 10.4. Adverse Events: Definitions and Procedures for Recording, Evaluating, Follow-up, and Reporting

### 10.4.1. Definition of AE

AE Definition

An AE is any untoward medical occurrence in a participant or clinical investigation participant administered a pharmaceutical product and which does not necessarily have to have a causal relationship with this treatment (ICH E2A).

Note: An AE can therefore be any unfavorable and unintended sign (including an abnormal laboratory finding), symptom, or disease [new or exacerbated] temporally associated with the use of the study drug, whether or not considered related to the study intervention.

Events Meeting the AE Definition

Any abnormal laboratory test results (hematology, clinical chemistry, or urinalysis) or other safety assessments (eg, ECG, radiological scans, vital signs measurements), including those that worsen from baseline, considered clinically significant in the medical and scientific judgment of the Investigator (ie, not related to progression of underlying disease).

Exacerbation of a chronic or intermittent pre-existing condition including either an increase in frequency and/or intensity of the condition.

New conditions detected or diagnosed after study intervention administration even though it may have been present before the start of the study.

Signs, symptoms, or the clinical sequelae of a suspected drug-drug interaction.

Signs, symptoms, or the clinical sequelae of a suspected overdose of either study intervention or a concomitant medication. Overdose per se will not be reported as an AE/SAE unless it is an intentional overdose taken with possible suicidal/self-harming intent. Such overdoses should be reported regardless of sequelae.

Events Not Meeting the AE Definition

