7.7.2. Adverse Events

The following definitions will be used for AEs:

- Pretreatment AEs: Any AE that starts after providing informed consent/assent, but before randomization or before the start of the first infusion of study drug.
- Treatment-emergent adverse event (TEAE): Any AE that starts between the first infusion of study drug and up to 8 months after the last infusion of study drug.
- Treatment-emergent serious adverse event (TESAE): A TEAE that is serious.

The incidence of TEAEs, TEAEs leading to withdrawal from the study, TEAEs leading to study treatment discontinuation, drug-related TEAEs, TEAEs during study drug administration, and SAEs will be summarized by treatment group. All AEs will be coded using MedDRA version 23 or higher and will be summarized by SOC and Preferred Term overall, severity, and relationship to treatment. Participants having multiple AEs within a category (eg, overall, SOC, Preferred Term) will be counted once in that category. For severity/relationship tables, the participant's highest grade/most related event within a category will be counted. Percentages will be based on the number of treated participants in the Safety Set within a treatment group and overall. Tables will be sorted by descending frequency of SOC and by descending frequency of Preferred Term within an SOC.

Detailed by-participant listings of pretreatment AEs, TEAEs, SAEs, related TEAEs, TEAEs during study drug administration, TEAEs leading to withdrawal from the study, and TEAEs leading to study treatment discontinuation will be provided.

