9.3.8. Adverse Events

TEAEs are events with start dates on or after the date of the start of the first infusion of study drug and up to 8 months after the last infusion of study drug. If the start date of an AE is partially or completely missing and the end (stop) date of the AE does not indicate that it occurred prior to first dose or 8 months after last dose, then the determination of treatment-emergent status will be based on the following:

- If the start year is after the year of the start of first infusion of study drug and before the year of last infusion of study drug, then the AE is treatment emergent.
- If the start year is the same as the year of the start of the first infusion of study drug and
 - The start month is missing, then the AE is treatment emergent

OR

- The start month is present and is the same or after the month of the first infusion of study drug, then the AE is treatment emergent
- If the start date is completely missing, then the AE is treatment emergent.

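### Treatment-emergent status rests on the AE start date alone, so a new AE that starts between consent and Day 1 and worsens, turns serious or stops treatment after dosing can fall outside the TEAE counts

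*Protocol*

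**What the plan says.** Both documents fix treatment-emergent status by when the event starts.

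- Protocol 9.4.2.1 calls an AE pretreatment if it is "Any AE that starts after providing informed consent, but before the first infusion of study drug" and treatment-emergent if it is "Any AE that starts between the start of the first infusion of study drug and up to 8 months after the last infusion".
- SAP 7.7.2 repeats the rule: "Any AE that starts between the first infusion of study drug and up to 8 months after the last infusion of study drug".
- SAP 9.3.8 turns it into a derivation: "TEAEs are events with start dates on or after the date of the start of the first infusion of study drug", with the same 8-month upper limit. Its sub-rules deal only with partial or missing start dates.
- A TESAE is a subset of TEAEs: "A TEAE that meets the criteria for serious" in Protocol 9.4.2.1 and "A TEAE that is serious" in SAP 7.7.2.
- All six event rows of the AE overview in SAP 7.7.2.1 are TEAE or TESAE rows. They include related events, withdrawal from the study and discontinuation of treatment.

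On collection and recording:

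- Protocol 8.4.1 states: "All AEs and SAEs will be collected from the signing of the ICF until the EOS Visit". Screening lasts up to 2 weeks before Day 1.
- Protocol 10.4.1 counts as an AE: "Exacerbation of a chronic or intermittent pre-existing condition including either an increase in frequency and/or intensity of the condition".
- Protocol 10.4.3 sends new or updated information about an event to the CRF record that was first completed.

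**The concern.** Participants enter with TMA and acute kidney injury, so new AEs between consent and Day 1 are foreseeable. If such an event worsens after the first infusion, the part of most interest for safety is the part that happened on treatment. A start-date rule assigns the whole event to the pretreatment period.

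This matters for a drug whose named risk is serious infection (Protocol 2.3.1 and Table 3), in a study where severe uncontrolled infection is a listed reason for stopping study drug (Protocol 7.1). There is no Data Monitoring Committee (Protocol 9.6), so the planned safety tables carry much of the assessment. An infection acquired during Screening that becomes severe after dosing and ends treatment would be missing from the rows where a reader would look for it.

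**Working it through.** The plan gives no figure on this point, so there is none to reproduce. The check applies the rules to cases.

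**Starting case.** A new AE has a complete start date after consent and before Day 1, and is kept on one CRF record. Protocol 10.4.3 points to updating that record, and neither document tells sites to open a new one when an AE worsens.

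| What happens after the first infusion | Class under Protocol 9.4.2.1, SAP 7.7.2 and 9.3.8 | Rows it is left out of | Where it can still appear |
|---|---|---|---|
| Rises in grade | Pretreatment | TEAE | Pretreatment-AE listing (SAP 7.7.2) |
| Becomes serious | Pretreatment | TEAE, TESAE | SAE listing and SAE summaries (SAP 7.7.2, 7.7.2.1, 7.7.2.2) |
| Leads to stopping study drug or leaving the study | Pretreatment | TEAE, TEAE leading to discontinuation or withdrawal | Primary reason in disposition (SAP 7.2.1) |

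**Where the gap does not arise.**

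- SAP 9.3.8 works on dates, so an event starting on Day 1 before the infusion counts as treatment-emergent.
- Unless the stop date rules it out, so does an event with a missing day in the month of the first infusion, a missing month in that year, or a wholly missing start date.
- If the site records the worsening as a separate AE with its own start date, that record is a TEAE.

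**Size per participant.** SAP section 4 gives 16 enrolled, randomized 1:1. The split by arm, and the number dosed, are not stated. Assume all were dosed and arms are equal: 16 / 2 = 8. One participant then moves a row by 1 / 8 = 12.5 percentage points. For arms of 9 and 7 the figures are 1 / 9 = 11.1 and 1 / 7 = 14.3 points.

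SAP 7.7.2 counts a participant once per category. The shift therefore occurs only if the misclassified event is that participant's sole event in the row. That is more plausible for the TESAE and discontinuation rows than for any TEAE, where a participant followed for months is likely to have another event.

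**Number of such events.** The documents give no basis for an estimate.

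**The case against.** The strongest reply is that little is hidden. The SAP lists pretreatment AEs and SAEs by participant, plans SAE summaries not labelled treatment-emergent, lists and counts deaths, lists AEs of special interest, and reports reasons for discontinuation by group. With 16 participants and no hypothesis testing, a reader can inspect every case. This stands against any claim that the events disappear from reporting. It does not correct the incidence rows, and the SAP does not say whether the unlabelled SAE summaries include pretreatment events. The protocol's own listings omit pretreatment AEs.

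A second reply is that much worsening is reportable as its own AE. A reader might infer from the exacerbation clause that only chronic or intermittent conditions qualify. The documents are broader:

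- Protocol 10.4.1 also covers clinically significant test results that worsen from baseline. It exempts day-to-day fluctuations of conditions present at the start only if they do not worsen.
- Protocol 9.4.2.2 and SAP 7.7.3.5 class adverse changes in physical examination as AEs.

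This narrows the gap. It does not settle whether an acute AE already on record gets a new start date. The CRF instructions are not among the documents, so the single-record premise is an assumption, though Protocol 10.4.3 favours it.

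A third reply concerns the infection trigger. A reader might infer that an enrolling infection that flares after dosing would be lost. Under inclusion criterion 4, TMA within the 14 days before Screening is already linked to its trigger, so a trigger infection normally predates consent. It is then a pre-existing condition. If its worsening after dosing is reported as an AE, the start date falls after the infusion and it is a TEAE. The case at issue is a new event that starts after consent.

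**Conclusion.** The point holds in a narrow form. By the stated rule in both documents, a new AE with a complete start date after consent and before Day 1 that worsens in grade, becomes serious or leads to stopping study drug after the first infusion, and is kept on one record, is left out of the TEAE, TESAE and TEAE-leading-to-discontinuation or withdrawal counts. The consequence is understated absolute incidence in those rows. With an assumed 8 treated per arm this is about 12.5 percentage points per affected participant (11.1 to 14.3 for arms of 9 and 7), and only where the participant has no other event in the row.

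A reader might also infer that the comparison between arms is biased in favour of ravulizumab. The documents do not support that. The rule is the same in both blinded arms, and the difference would be understated only if such worsening were more common on ravulizumab, which cannot be derived here.

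**What to change.** In SAP 7.7.2 and 9.3.8, define a TEAE as any AE that starts, or any pretreatment AE that worsens in CTCAE grade or becomes serious, on or after the start of the first infusion and up to 8 months after the last. Align Protocol 9.4.2.1 for consistency. Count AEs leading to study drug discontinuation or study withdrawal whatever their onset date.

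Enrollment is closed, so a new data-entry instruction cannot reach Screening data already collected. The practical change is to the SAP derivation, using whatever dated grade, seriousness and action-taken data are on the database. SAP version 2.0 still carries a placeholder date and describes the final analysis as yet to be done, so the cost is a few lines of text and programming.

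There are two small downsides. AE incidence may rise slightly in both arms, and worsening can be identified only where a dated change was recorded.

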#### **9.4.2.2. Physical Examination and Vital Signs**

Adverse changes from baseline in physical examination findings will be classified as AEs and analyzed accordingly.

Vital signs will be summarized descriptively by treatment group at baseline and post-baseline time points and for changes from baseline.

#### **9.4.2.3. Clinical Laboratory Tests**

Observed values and changes from baseline in clinical chemistry, hematology, and spot urine collection will be summarized descriptively by treatment group at baseline and at each post-baseline time point. For laboratory results that can be classified as normal, low, or high based on normal range values, shifts from baseline in classification will be summarized for all study visits.

#### **9.4.2.4. Electrocardiograms**

By-participant data listings of ECG parameters will be provided separately for each disease cohort. Electrocardiograms will be evaluated and summarized as normal, abnormal not clinically significant, or abnormal clinically significant. A shift from baseline to worst on-study ECG table will be presented for ECG results. Observed values and change from baseline in ECG intervals (PR, RR, QT, and QTc) will be summarized descriptively at baseline and each postbaseline time point. The QT interval will be corrected for heart rate using Fridericia's formula (QTcF).

#### **9.4.2.5. MACE**

Descriptive statistics for number and percentage of participants with MACEs will be presented by treatment group. Pre-treatment and treatment-emergent MACE rates through Day 183 (Week 26) (number per 100 participant-years) along with participant-years of follow up and total number of MACEs will be displayed by treatment group. MACE is defined in Section 8.4.5.

#### **9.4.3. Pharmacokinetic/Pharmacodynamic Analysis**

Individual PK/PD data will be collected for all participants.

Graphs of mean serum ravulizumab concentration-time profiles will be constructed. Graphs of serum concentration-time profiles for individual participants may also be provided. Descriptive statistics will be calculated for serum concentration data at each sampling time, as appropriate.

The PD effects of ravulizumab will be evaluated by assessing the absolute values and changes and percentage changes from Baseline in serum free C5 concentrations over time, as appropriate. Descriptive statistics will be calculated for the PD data at each sampling time, as appropriate.

#### **9.4.4. Immunogenicity Analyses**

The incidence of ADAs to ravulizumab will be presented at each postbaseline time point in tabular format. Additionally, any confirmed ADA-positive samples will be tested for titer and the presence of neutralizing antibodies to ravulizumab.

#### **9.4.5. Exploratory Analyses**

The exploratory efficacy analyses will be descriptive in nature and will be based on the mITT Set. Full details regarding the exploratory analyses will be described in the SAP.

##### **9.4.5.1. Quality of Life**

The following quality of life assessments will be summarized by treatment group at baseline and each postbaseline time point using descriptive statistics for the observed value as well as the change from baseline:

- EQ-5D-5L
- KDQOL-36

##### **9.4.5.2. Other Exploratory Endpoints**

Analyses of exploratory biomarkers and genetic testing will be described in separate SAPs and may be summarized after study completion.

### **9.5. Planned Analyses**

#### **9.5.1. Interim Analysis**

An interim analysis to assess sample size re-estimation will be performed when 50% of the planned participants ( $n = 100$ ) have been assessed for the primary estimand. This interim analysis will be performed by an unblinded independent statistical center that is not involved with study conduct or final analysis of study data. Enrollment of participants will proceed without interruption while the analysis is ongoing. There are no plans to stop the study for demonstration of efficacy or futility at the interim analysis.

The sample size re-estimation analysis will be based on the conditional power calculated using the results obtained at this interim analysis. If the conditional power falls within the promising zone based on the estimated treatment effect, the sample size will be increased up to a maximum of 150 participants. Because the total sample size could potentially be increased in a data-dependent manner following the interim analysis, the final primary analysis for the primary estimand will be tested using the Cui, Hung, Wang method for controlling the type 1 error (Cui, 1999). Full details will be provided in a separate interim SAP.

### **9.5.2. Primary Efficacy Analysis**

The primary efficacy analysis will be performed at the end of the 26-Week Treatment Period after all participants have completed or withdrawn from the 26-Week Treatment Period. This analysis will allow for evaluation of the primary estimand.

### **9.5.3. Final Analysis**

The final study analysis will be conducted at the end of the study (Section [4.5](#)). The SAP will describe the planned analysis in greater detail.

## **9.6. Data Monitoring Committee**

This study will not include a Data Monitoring Committee.

## **10. SUPPORTING DOCUMENTATION AND OPERATIONAL CONSIDERATIONS**

### **10.1. Regulatory, Ethical, and Study Oversight Considerations**

#### **10.1.1. Regulatory and Ethical Considerations**

- This study will be conducted in accordance with the protocol and the following:
  - Consensus ethical principles derived from international guidelines including the Declaration of Helsinki and CIOMS International Ethical Guidelines
  - Applicable International Council for Harmonisation of Technical Requirements for Pharmaceuticals for Human Use (ICH) Good Clinical Practice (GCP) Guidelines
  - Applicable laws and regulations
- The protocol, substantial protocol amendments, ICF, IB, and other relevant documents (eg, advertisements) must be submitted to an IRB/IEC by the Investigator/Alexion and reviewed and approved by the IRB/IEC before the study is initiated.
  - If any of these documents require regulatory/health authority approval per local regulations, Alexion will also obtain such approval before the study is initiated.
- Any substantial amendments to the protocol will require IRB/IEC and regulatory/health authority approval before implementation of changes made to the study design, except for changes necessary to eliminate an immediate hazard to study participants.
- The Investigator will notify the IRB/IEC of deviations from the study protocol or GCP as defined by applicable law as a serious breach or as required by IRB/IEC procedures.
- The Investigator will be responsible for the following:
  - Providing written summaries of the status of the study to the IRB/IEC annually or more frequently in accordance with the requirements, policies, and procedures established by the IRB/IEC
  - Notifying the IRB/IEC of SAEs or other significant safety findings as required by IRB/IEC procedures
  - Providing oversight of the conduct of the study at the site and adherence to requirements of 21 CFR, ICH guidelines, the IRB/IEC, Directive 2001/20/EC, European regulation 536/2014 for clinical studies (if applicable), and all other applicable local regulations

